3.0 Inclusion/Exclusion Criteria

Inclusion Criteria: Subjects who meet the following inclusion criteria will be considered for participation in formative focus groups:

- a) Self-identify as male
- b) Age 18-35
- c) Have sex with men
- d) Currently taking PrEP
- e) Own a smartphone
- f) Would like to participate in a focus group to provide feedback on a mobile app to support PrEP adherence

Inclusion Criteria: Subjects who meet the following inclusion criteria will be considered for participation in the RCT:

- a) Self-identify as male
- b) Age 18-35
- c) Have sex with men
- d) Currently taking PrEP
- e) Own a smartphone and would like support for taking PrEP

Exclusion criteria: Those who meet any of the following criteria will be excluded from participation in formative focus groups:

- a) Males who do not meet the above criteria
- b) Currently use I.V. drugs

Exclusion criteria: Those who meet any of the following criteria will be excluded from participation in the RCT:

- a) Males who do not meet the above criteria
- b) Currently use I.V. drugs

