5.0 Study Procedures

The proposed study will include 2 zoom focus groups of 6-8 individuals each (or zoom interviews with the same number of individuals), which will solicit feedback on text messages and the usability of the prototype app and be approximately 2 hours long, and a randomized control trial (RCT) to evaluate the effectiveness of the DOT intervention on PrEP adherence among young adult MSM on PrEP. For the RCT, those who meet study criteria will complete online baselines in Qualtrics, then be randomized by Qualtrics to either the intervention group (DOT mobile app) or the control group (2page document offering PrEP adherence education).

Study procedures:

Formative Focus Groups/Interviews: After signing an online informed consent form, individuals will meet together for a 2 hour conversation (either in a focus group or interview), during which they will provide feedback on new text messages and the usability of the prototype app. Focus groups will be audiotaped. Participants will receive a \$75 Amazon gift card at the end of the focus group.

RCT (both arms): Those who consent to the RCT will automatically receive a link to collect demographic data, e.g. age, ethnicity, education, income, and length of time on PrEP, and the baseline assessments. Qualtrics will then randomize participants to the intervention or control arm. Intervention and control participants will be offered a \$20 Amazon gift card for completing baselines. At study completion (12 weeks), all participants will receive a text and email informing them that it is time to re-take baseline assessments. After completion, they will receive a \$155 Amazon gift card.

RCT Intervention Group: Intervention participants will receive a link to download the DOT mobile app from our website. During the 12-week study period, intervention participants will receive 3 types of messages: pill reminders, educational, and motivational (including new ones targeting stress). The

Protocol #2 R44 MH112221-02

Version: 3

November 23, 2020

DOT app will also include a link to the DOT online community (with online community rules that each participant must agree to before become a part of the community) and a “GET HELP NOW” link to the federal crisis intervention program. We have attached the online community rules for IRB review.

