Measures. Both baseline (T1) and 12-week follow up (T2) data will be collected on the following key measures: **Primary outcome measure:** The primary outcome compares differences between (T1) and (T2) for the key measure of interest: PrEP adherence: Our Phase 1 open-ended data revealed participants' general discomfort with blood tests and needles. Thus, we will not seek PrEP blood levels in Phase 2 to measure adherence as doing so would likely pose a barrier to recruitment and retention. Instead, we will use Wilson's simple 3-item self-report adherence measure which showed good psychometric characteristics and good construct validity when compared with an electronic drug monitoring standard, for both HIV and non-HIV medications, and has been validated with culturally-diverse patient groups, including MSM (Fowler et al., 2014; Wilson et al., 2014; 2016). The items include: 1) In the last 30 days, on how many days did you miss at least one dose of any of PrEP (write in # of days) 2) In the last 30 days, how good a job did you do at taking your PrEP in the way you were supposed to? (6-point Likert) 3) In the last 30 days, how often did you take your PrEP in the way you were supposed to? (6-point Likert). Note: We will also examine self-report app adherence data. App adherence data can only be collected via the app as yes or no responses to pill reminders, and thus cannot serve as pre-intervention baseline. We will, however, compare app adherence data from weeks 1 and 12.

Consideration of Relevant Biological Variables: We will only include culturally-diverse young adult males who have sex with other males in our study as they are disproportionately represented among groups at increased risk for HIV. Moreover, males account for 95.3% of all PrEP users (Huang et al., 2018).

Mediating Variables: We propose four mediating variables: PrEP self-efficacy, intention to follow PrEP guidelines, PrEP knowledge and stress burden. To measure PrEP treatment self-efficacy, we will use the **Adherence Self-Efficacy Scale** (ASES) (Johnson et al., 2007). It is a 12-item scale of patients' confidence to carry out

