Perceived stress burden will be included as a potential mediating variable for two reasons: First, the intervention targets stress burden via supportive texts and an online community. Second, reductions in perceived stress can facilitate medication adherence (Stewart et al., 2005). Stress burden will be assessed using the 10-item **Perceived Stress Scale** (Cohen et al., 1983), which has been validated with a wide-range of patient and non-patient groups (e.g. Chiu et al., 2016; Perera et al., 2017). We will analyze psychometric properties and construct validity on the two new measures (intention to follow guidelines and PrEP knowledge) as a part of our Phase 2 analyses.

Moderating Variable. Length of time on PrEP (in months) will be included as a moderator as it seems possible that the greater the length of time on PrEP, the more likely a participant has developed personal strategies to support adherence or have supports (family members, friends, healthcare providers) in his social environment that help with adherence.

Demographic and Control Variables. T1 assessments will also gather a number of demographic indicators, including age, years of education, income and, as mentioned above, length of time on PrEP. Income will be coded categorically from 1 to 7 in relation to the federal poverty level: <100% (1), 100%-149% (2),

150%-199% (3), 200%-249% (4), 250%-299% (5),
300%-349% (6), 350%-399% (7), and $\geq 400\%$.

Randomization: Participants will be randomly assigned to intervention or control group via the randomizer function on Qualtrics software. **Sample size:** We will aim to recruit and gain consent from 110 participants (55 each for intervention and control arms). **Power analysis:** Based on our Phase 1 pretest results, an a priori power analysis for a multiple regression with 4 predictors of PrEP adherence was conducted to determine a sample size with a power of at least 90% with a two-sided alpha level of .05. The desired minimum sample size was 92 participants (Rosner, 2010). In the event of 20% attrition, we added 20% additional participants to the sample, and set 110 as the total sample size. Therefore, even if the study encounters diminished recruitment or greater post-recruitment attrition, it should still be possible to detect moderate effects.

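### Adherence at T1 is known before assignment, yet no blocking or stratification is specified and Hypothesis 1 uses T1 adherence either not at all or only as a change score

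*SAP*

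**What the plan says.** **Order of events.** Protocol 5.0 puts the baseline first: "those who meet study criteria will complete online baselines in Qualtrics, then be randomized by Qualtrics to either the intervention group". It repeats the order for both arms: "Qualtrics will then randomize participants to the intervention or control arm". The SAP's Measures section lists adherence, a 3-item self-report that includes missed days in the last 30, among the variables measured at both times: "Both baseline (T1) and 12-week follow up (T2) data will be collected on the following key measures".

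**Allocation.** The SAP's Randomization paragraph says only: "Participants will be randomly assigned to intervention or control group via the randomizer function on Qualtrics software". The Sample size sentence after it sets a target: "We will aim to recruit and gain consent from 110 participants (55 each for intervention and control arms". Neither document mentions blocks, strata, minimisation or an even-allocation setting.

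**Who can enter.** Protocol 3.0 sets no level of adherence for the RCT. The nearest criterion is "Own a smartphone and would like support for taking PrEP". A man who reports no missed day can enrol.

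**Analysis.** Under Hypothesis 1, Model 1 contains treatment alone and Model 2 adds age, education and income. Model 3 adds time and a treatment-by-time interaction, so its coefficient is the difference between arms in change. No model is named primary. The Data Analysis paragraph compares the arms on all T1 variables, and significant differences lead only to discussion.

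**The concern.** T1 adherence is likely to be the strongest available predictor of T2 adherence, and it sits in the same system before allocation. The plan does not say that it is used to balance the arms, and Models 1 and 2 do not use it in the analysis.

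The outcome also has a ceiling. A man with 0 missed days at T1 cannot improve on item 1. If one arm happens to hold more such men, it has less room to show a gain.

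Two things are at stake. The first is precision that could be had from data already collected. The second is a clear answer to Hypothesis 1: a chance difference at T1 pushes the 12-week comparison and the change comparison in opposite directions, and the plan does not say which one decides.

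**Working it through.** **The plan's own figure.** 92 x 1.2 = 110.4, which gives the stated 110, or 55 per arm. The 92 cannot be checked, because no effect size is given for the power calculation ("an a priori power analysis for a multiple regression with 4 predictors of PrEP adherence was conducted", "with a power of at least 90% with a two-sided alpha level of .05").

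**Inputs.** From the documents: N = 110 with a 1:1 target. Assumed: simple randomisation; T1-T2 correlation r = 0.6 (range 0.3-0.7) with equal SDs at T1 and T2; 30-50% of men with no missed day at T1.

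**1. Chance difference in mean T1 adherence, in SD units**
- SD of the difference between arms = sqrt(2/55) = 0.191.
- Chance that it exceeds 0.2 SD in either direction: 0.2/0.191 = 1.05, so 29%. Chance that it exceeds 0.3 SD: 12%.
- 95% limit: 1.96 x 0.191 = 0.37 SD.
- A baseline t-test becomes significant only above about 1.98 x 0.191 = 0.38 SD, so the planned comparison would usually not flag imbalances of 0.2-0.37 SD.

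**2. What an imbalance does to each model**

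For an imbalance D, a T2-only contrast moves by r x D and a change contrast by (r - 1) x D. The Model 2 figure assumes that age, education and income explain little of T1 adherence.

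| D = 0.2 SD | r = 0.3 | r = 0.6 | r = 0.7 |
|---|---|---|---|
| Models 1 and 2 | +0.06 | +0.12 | +0.14 |
| Model 3 | -0.14 | -0.08 | -0.06 |

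Without covariates, the T2-only and change estimates differ by exactly D, whatever r is. At the 95% limit of 0.37 SD, the shift in Models 1 and 2 is 0.11-0.26 SD for r from 0.3 to 0.7.

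**3. Men with no missed day at T1**

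SD of the difference in share = sqrt(2p(1 - p)/55).
- p = 0.3: SD 0.087; chance of a gap above 10 percentage points 25%.
- p = 0.5: SD 0.095; chance 29%.

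Forcing 55:55 without strata barely changes these SDs (0.088 and 0.096 by simulation), so blocking alone does not help. Simulated blocks of 4 within two T1 strata, with 20-70% of men having room to improve, hold the gap to at most 1.8-2.9 points and arm sizes to 54-56.

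**4. Arm sizes**
- Under Binomial(110, 0.5), exactly 55:55 has probability 7.6%, a split of 60:50 or worse 39%, and the 95% range for one arm is 45-65.
- Taking d = 0.683, back-solved so that 46:46 has 90% power, power is 94.4% at 55:55 and 93.7% at 45:65. At N = 92 it is 90.0% at 46:46 and 88.9% at 37:55.

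**5. What adjustment gains (r = 0.6)**
- T2 only: SE = 0.191.
- Change score: 0.191 x sqrt(2(1 - 0.6)) = 0.171.
- Two-level T1 stratum, stratified and modelled, split at the median of a normal score: 0.168 by simulation.
- Continuous T1 score as covariate, no stratification: 0.191 x sqrt(1 - 0.36) = 0.153.

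**The case against.** The strongest reply is that the plan already uses T1. The SAP defines the primary outcome as a comparison of T1 with T2, and Model 3 matches that definition by subtracting T1. A reader might infer that a T1 imbalance passes unchanged into all three models; the documents do not support that. What stands against the reply is that subtraction takes off the whole imbalance when only the fraction r carries over to T2. Model 3 therefore moves the other way, and it leaves a ceiling effect untouched.

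A second reply is that chance imbalance is not bias. This is right. The ordinary standard error of 0.191 SD already covers it, and a 0.12 SD shift lies well inside the resulting interval. The type I error rate is unaffected. The loss is in precision and in how the results can be read.

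A third reply is that silence does not show simple randomisation. This also stands. The randomizer may be set to give even arms, and the SAP aims for 55 each. A reader might infer that assignment is unrestricted, but the documents support only that no restriction is specified. The probabilities for arm sizes depend on that assumption.

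Finally, men who want support may be less often at the ceiling. The documents give no share, so 30-50% is illustrative.

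**Conclusion.** The point holds in a limited form. T1 adherence is available before assignment, no balancing on it is specified, and no Hypothesis 1 model uses it as a covariate.

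The cost is precision and possible disagreement between models. At r = 0.6, covariate adjustment would cut the standard error from 0.191 to 0.153 SD, and a 0.2 SD imbalance puts a gap of 0.20 SD between the T2-only and change estimates. An imbalance of that size or larger arises in about 29% of trials.

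These sizes rest on an assumed correlation. The figures for men with no missed day also need an assumed ceiling share and simple randomisation. The absence of a specified stratum and of a T1 covariate rests on the documents alone.

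Two stronger readings should be set aside. One is that the trial is biased, which chance imbalance under randomisation does not cause. The other is that unequal arms threaten power: within the 95% range of splits the loss is about 1 point.

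**What to change.** 1. **Analysis.** Add the continuous T1 adherence score, scored in the same way as T2, as a covariate in the Hypothesis 1 model of T2 adherence, and name that model primary. This can be done even if enrolment has begun, provided that it is fixed before the data are analysed.
2. **Allocation, if enrolment has not opened.** State the randomizer setting. Branch on T1 item 1 (0 versus 1 or more missed days) before the randomise step, balance assignment within each branch, and keep the stratum in the model. Check first that the survey software can do this with concealed assignment; the documents do not show it.
3. **Collinearity rule.** The SAP keeps only one of two similar variables correlated above 0.4. The stratum is a cut of one T1 item and may well exceed that, so state that the rule does not apply to the stratum and the T1 score.

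The cost is one or two model terms, a survey-flow branch and a few SAP sentences. Step 1 matters most: the continuous score alone does better than stratification with only a stratum term (0.153 against 0.168).

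An estimate among men with 1 or more missed days is optional. With 30-50% at the ceiling it would rest on 110 x 0.5 = 55 to 110 x 0.7 = 77 men, with 44-58% power for an assumed 0.5 SD effect before attrition, so it should be labelled as low-powered.

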8.0 Statistical Considerations

The sample size of 110 for the RCT is based on our Phase 1 pretest results and an a priori power analysis for a multiple regression with 4 predictors of PrEP adherence, which was conducted to determine a sample size with a power of at least 90% with a two-sided alpha level of .05. The desired minimum sample size was 92 participants (Rosner, 2010). In the event of 20% attrition, we added 20% additional participants to the sample, and set 110 as the total sample size. Therefore, even if the study encounters diminished recruitment or greater post-recruitment attrition, it should still be possible to detect moderate effects.

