Analysis plan:

Data Analysis: Analyses will be performed using SPSS version 22 to run diagnostics (tests for normality, multicollinearity, heteroscedasticity) to assess violations of analytic assumptions, univariate statistics, bivariate tests, and multivariate linear regression. Because study retention may be influenced by preconditions, t-tests or Wilcoxon test will be used to compare intervention group and control group on all T1 variables. T- tests can be used for normal distribution while Wilcoxon test can be used in skewed distribution. Implications of significant differences will be discussed. Based on the intent to treat approach, missing T2 data will be imputed to retain all participants in analyses. We will include all participants who provide informed consent and engage in the T1 assessment, regardless of what portion of the assigned treatment or control protocol is completed. Data will be imputed using multiple imputation for participants who fail to complete the T2 (posttest) assessment.

Sensitivity analyses will explore the implications of the imputation methods employed (e.g., multiple imputation, propensity score matching). Post- recruitment attrition (loss of potential participants who were recruited but failed to engage in any assessments or part of the treatment or control protocol) will be explored in all discussion and implications of study findings. The following series of regressions will assess study hypotheses.

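### Adding 20% to 92 does not cover 20% attrition: 110 enrolled leaves 88, four below the plan's own minimum

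*SAP*

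**What the plan says.** The SAP (Sample size and Power analysis) and Protocol 8.0 give the same derivation. A power analysis for a regression with four predictors, at two-sided alpha .05 and power of at least 90%, leads to this: "The desired minimum sample size was 92 participants". The allowance follows: "In the event of 20% attrition, we added 20% additional participants to the sample, and set 110 as the total sample size". The SAP describes the total as a number at consent: "We will aim to recruit and gain consent from 110 participants", split 55 per arm.

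Both documents then draw a conclusion from the allowance: "even if the study encounters diminished recruitment or greater post-recruitment attrition, it should still be possible to detect moderate effects". The SAP's Data Analysis section defines post-recruitment attrition as "loss of potential participants who were recruited but failed to engage in any assessments or part of the treatment or control protocol".

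On missing follow-up, the same section says "We will include all participants who provide informed consent and engage in the T1 assessment", and that "missing T2 data will be imputed to retain all participants in analyses", by multiple imputation.

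**The concern.** The allowance is there so that the minimum of 92 survives a 20% loss. Adding 20% to the target does not achieve that, because the 20% is lost from the larger, enrolled number. A reader would reasonably take 92 as protected at 20% attrition, and it is not.

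The next sentence makes this slightly worse. It is worded as a consequence of the allowance and extends to greater attrition, although the allowance does not fully cover the rate it names. That sentence attaches no power level to its remark about moderate effects, so the remark is not shown to be false. What lacks support is the step from the allowance to it.

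At stake is a small loss of power against the plan's own target of at least 90%, and an inaccurate statement of how much loss the trial can absorb.

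**Working it through.** **Inputs** (SAP, Sample size and Power analysis; Protocol 8.0): minimum 92; attrition 20%; total 110; power at least 90%; two-sided alpha .05; four predictors. No effect size is stated.

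**1. Reproducing the plan's figure.** 92 × (1 + 0.20) = 110.4, set to 110. The stated total is reproduced.

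**2. What 110 delivers.**
- Loss at 20%: 110 × 0.20 = 22, and 110 − 22 = 88 remain.
- Shortfall: 92 − 88 = 4.
- Losses covered: 110 − 92 = 18, and 18/110 = 16.4%.
- Total that keeps 92 at 20% loss: 92/(1 − 0.20) = 115, which is 5 more than 110. Equal arms need 116 (58 each).

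**3. Power at 88, complete cases.** This is conditional, because the effect size has to be assumed. Noncentral F test, alpha .05, noncentrality f² × N, error degrees of freedom N − 5. If 92 is the smallest N that reaches 90%, f² lies between the value giving exactly 90% at 92 and the value giving exactly 90% at 91.

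| Test | f² giving 90% at 92 | Power at 88 | f² giving 90% at 91 | Power at 88 |
|---|---|---|---|---|
| Joint test of 4 predictors | 0.1768 | 88.4% | 0.1789 | 88.8% |
| Single coefficient | 0.1168 | 88.7% | 0.1181 | 89.0% |

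Break-even: 88 still gives 90% if power at 92 was already about 91.5% (joint test, f² = 0.1854) or 91.3% (single coefficient, f² = 0.1222).

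**4. What imputation can recover.** Large-sample approximation with many imputations, data missing at random, T1 adherence in the imputation model, and equal T1 and T2 variances:

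1/N_eff = (1 − R²)/88 + R²/N_T1

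Here N_T1 is the number with T1 data, and r is the T1–T2 correlation of adherence. R² = r² if the outcome is T2 adherence alone (the first and second regression models under Hypothesis 1). R² = (1 − r)/2 if it is T1–T2 change (the third model, and the SAP's Measures section: "The primary outcome compares differences between (T1) and (T2) for the key measure of interest").

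Example: all 22 lost after T1 (N_T1 = 110), r = 0.5, T2 outcome. R² = 0.25, so 1/N_eff = 0.75/88 + 0.25/110 = 0.010795 and N_eff = 92.6.

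| Losses (of 22) | Outcome | r = 0 | r = 0.3 | r = 0.5 | r = 0.7 |
|---|---|---|---|---|---|
| All after T1 | T2 only | 88.0 | 89.6 | 92.6 | 97.6 |
| All after T1 | Change | 97.8 | 94.6 | 92.6 | 90.7 |
| Half before T1 | T2 only | 88.0 | 88.9 | 90.5 | 93.1 |
| Half before T1 | Change | 93.2 | 91.6 | 90.5 | 89.5 |
| All before T1 | Either | 88.0 | 88.0 | 88.0 | 88.0 |

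With all losses after T1, reaching 92 needs R² = (1/88 − 1/92)/(1/88 − 1/110) = 0.217. That means r of about 0.47 or more for a T2 outcome, but about 0.57 or less for change. The direction reverses, so no single correlation threshold settles the matter.

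**The case against.** The best counter-argument is that 88 is not the planned analysis size. The SAP keeps everyone with T1 data and imputes T2. If all 110 complete T1 and the T1–T2 correlation is 0.5, the effective size is 92.6 for either outcome and nothing is lost. This stands as a possibility but not as a guarantee, as the table shows. Nor does the sample-size text rely on imputation; it justifies 110 by head count alone.

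A second objection concerns where the 110 is counted. The SAP speaks of consent, but the same sentence gives 55 per arm, and Protocol 5.0 places randomization after the baseline assessment. On that reading all 110 have T1 data and the rows with losses before T1 fall away. The wording is ambiguous. The main arithmetic does not depend on it: 20% of 110 is 22 on either reading.

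Third, the plan never says in so many words that 92 will remain after a 20% loss, and it names no comparator for greater attrition. Both are inferences. The first follows naturally from the purpose the sentence gives for adding the 20%. The second is less certain, since the defined term covers people who take part in nothing, and the plan does not say which kind of loss the 20% refers to.

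Finally, the effect is small: about 1.0 to 1.6 percentage points of complete-case power under the assumption used. That is accepted and sets the weight of the point.

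**Conclusion.** The concern holds, as a minor one. The allowance is 4 short in participants with outcome data (88 against 92), or 5 short in enrolment (110 against 115). It covers 16.4% attrition, not 20%. These figures rest only on the plan's own numbers.

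The power figures are conditional. They assume that 92 is the smallest size reaching 90%, and they describe a complete-case analysis. If the original calculation had a little power to spare at 92, then 88 could still reach 90%. The shortfall would not by itself change how a result is read.

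**What to change.** Keep 110 and correct the text in both Protocol 8.0 and the SAP.

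- Replace the allowance sentence with: *A total of 110 retains at least 92 participants with up to 18 losses (16%); at 20% attrition 88 remain, for which power is [sponsor to recompute from its Phase 1 effect size].*
- Amend the robustness sentence so that it does not present the allowance as covering attrition above 20%, for example: *If more than 18 of the 110 are lost, before or after T1, fewer than 92 will have outcome data.* This is true wherever the 110 is counted.

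The cost is a text change in two places and one power calculation by the sponsor, with no extra participants. If the sponsor prefers to hold 92 at 20% attrition, the total becomes 115 (5 more), or 116 for equal arms (6 more).

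### The sample size statement loses its own attrition margin: 110 less 20% leaves 88, below the stated minimum of 92, and the test and effect size behind 92 are not given

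*SAP*

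**What the plan says.** Protocol 8.0 (Statistical Considerations) and the power analysis at the end of the SAP give the same account. The size rests on "an a priori power analysis for a multiple regression with 4 predictors of PrEP adherence", with at least 90% power, "with a two-sided alpha level of .05". The source of the effect size is given only as "Based on our Phase 1 pretest results". The result is: "The desired minimum sample size was 92 participants". To cover 20% attrition, 20% is added and the total set at 110, or 55 per arm. Both documents then conclude that under weaker recruitment or heavier attrition "it should still be possible to detect moderate effects".

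Neither document gives an effect size, SD or R², says which test was powered, or defines moderate.

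Under Hypothesis 1 the SAP fits three regressions. Model 1 has treatment alone. Model 2 adds age, education and income. Model 3 adds a before/after indicator and its interaction with treatment. In each, one coefficient answers the hypothesis: treatment in models 1 and 2, the interaction in model 3. Missing T2 data are to be multiply imputed.

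**The concern.** Two things look wrong.

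First, the closing sentence claims a reserve against losses beyond those planned for, but the inflation does not fully cover the planned loss itself. Adding 20% to 92 is not the same as recruiting enough for 92 to remain after 20% are lost.

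Second, this is the plan's only statement of what the trial can detect, and it cannot be tied to the treatment effect. An overall test of four predictors can reach significance through age, education and income alone, so power for that test does not answer Hypothesis 1. If one coefficient was powered instead, the reader needs the between-arm difference that 92 implies. Without either, a reader facing a non-significant result cannot tell which sizes of benefit the trial was equipped to find.

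**Working it through.** **Inputs from the documents.** Minimum N = 92; target N = 110 in two equal arms; attrition 20%; power at least 90%; two-sided alpha 0.05; 4 predictors. **Assumed, because not given:** the test powered and the meaning of moderate.

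**1. Attrition step.**
- The plan's figure reproduces as 92 × 1.2 = 110.4, set at 110.
- Completers after 20% loss: 110 × 0.8 = 88, which is 4 short of 92.
- Recruitment needed to keep 92: 92 / 0.8 = 115.
- Loss that 110 tolerates: 1 − 92/110 = 16.4%.

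**2. What 92 corresponds to.** The documents give no effect size, so 92 cannot be derived forward. Solving backwards with the noncentral F distribution (noncentrality f² × N, denominator df = N − 5):
- Overall test, numerator df 4: 90% power at 92 needs f² = 0.177, so R² = 0.177/1.177 = 0.15. At f² = 0.15 the same test has 84% power at 92 and 82% at 88, and needs 108 for 90%.
- Single coefficient, numerator df 1: 90% power at 92 needs f² = 0.117. For a balanced two-arm indicator f² = d²/4, so d = 2 × √0.117 = 0.68 SD.

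**3. Power at 88 if it was 90% at 92.** Holding each back-solved effect fixed gives 88.4% for the overall test and 88.7% for the single coefficient.

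**4. Treatment coefficient in model 2.** Noncentral t, df = N − 5, noncentrality d × √(N/4), covariates explaining no variance. At N = 88 and d = 0.5 the noncentrality is 0.5 × √22 = 2.35.

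| N analysed | Power, 0.5 SD | Power, f² = 0.15 on this coefficient | Difference detectable with 90% power |
|---|---|---|---|
| 88 | 64% | 95% | 0.70 SD |
| 92 | 66% | 96% | 0.68 SD |
| 110 | 74% | 98% | 0.62 SD |

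An f² of 0.15 on this coefficient equals d = 2 × √0.15 = 0.775 SD.

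**5. Sensitivity for 0.5 SD, from 88 to 110 analysed (normal approximation).**
- Demographics explain 5% of variance: 67-77%. They explain 20%: about 74-83%.
- T1-T2 change, SD multiplied by √(2(1 − ρ)): 51-60% at ρ = 0.3, 65-75% at ρ = 0.5, 86-92% at ρ = 0.7.
- Model 3 fitted as pooled least squares ignoring the pairing, SD multiplied by √2: 38-46%.

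**The case against.** A reader might infer that the plan promises 90% power for a 0.5 SD effect and delivers only 64-74%. The documents do not support that reading, for three reasons.

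- **No power level is attached to moderate effects.** The 90% belongs to the calculation that gave 92. The closing sentence says only that detection should remain possible.
- **Moderate is undefined.** In a regression paragraph it could mean f² = 0.15. Placed on the treatment coefficient, that has 95-98% power at 88 to 110 and needs only 73 participants for 90%. It equals 0.775 SD, which many would call large for a two-arm difference, but that sets one convention against another.
- **The overall test is not established as the source of 92.** Model 2 itself has four predictors (treatment, age, education, income), so the calculation may have targeted the treatment coefficient. If Phase 1 suggested about 0.68 SD, then 92 is correct for that purpose.

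Nor does the SAP name model 2 as primary. Its Measures section describes the primary outcome as a T1-T2 difference, and step 5 shows how far power moves with the model and the T1-T2 correlation. Any single figure for 0.5 SD is therefore an illustration.

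All of this stands. It does not rescue the attrition step, which uses only the plan's own numbers. Multiple imputation is not an answer either: it keeps participants in the analysis but does not by itself restore the T2 information they did not provide.

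**Conclusion.** The point holds in limited form. At exactly the attrition the plan assumes, completers fall to 88, below its minimum of 92, so the assurance about heavier losses does not follow. This needs no assumption about effect size. The direct cost is small: about 88-89% power in place of 90%, whichever of the two tests was used.

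The larger gap is in reporting. The tested parameter, the effect size and the meaning of moderate are all missing. As an overall test, 92 reflects R² of about 0.15, part of which could come from demographics. As a single coefficient it reflects about 0.68 SD between arms. Power of 64-74% for 0.5 SD is conditional on that reading of moderate, on model 2 and on covariates explaining nothing. Nothing here shows 92 to be a wrong calculation, because the Phase 1 inputs are not in the documents.

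**What to change.** In Protocol 8.0 and the SAP power analysis:

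1. Name the test and coefficient that were powered, the effect size and SD taken from Phase 1, and the assumed covariate or T1-T2 correlation.
2. Give power or detectable difference for the treatment coefficient at 88 and at 110. For example: *88 completers give 90% power for a between-arm difference of about 0.70 SD, assuming no variance explained by covariates.* If Phase 1 supplies a T1-T2 correlation and T1 adherence enters the model, recompute on that basis.
3. Correct the attrition step to say that 20% loss from 110 leaves 88, below 92.
4. Delete the moderate-effects sentence, or replace it with the figures from item 2.

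The cost is a wording change in two documents, with no added participants. The stated figure becomes slightly less favourable.
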